- Have symptomatic herpes simplex at the time of randomization.
- Have had symptomatic herpes zoster infection within 12 weeks prior to randomization.

Approval Date: 3/16/2022
Principal Investigator: [name]
Application Number: IRB00262268

- Have a history of disseminated/complicated herpes zoster (for example, ophthalmic zoster or CNS involvement).
- Have a positive test for hepatitis B virus (HBV) defined as:
 - a. positive for hepatitis B surface antigen (HBsAg), or
 - b. positive for hepatitis B core antibody (HBcAb) and positive for hepatitis B virus deoxyribonucleic acid (HBV DNA)

Note: Patients who are HBcAb-positive and HBV DNA-negative may be enrolled in the study but will require additional HBV DNA monitoring during the study.
- Have hepatitis C virus (HCV) infection (hepatitis C antibody-positive and HCV ribonucleic acid [RNA]-positive).

Note: Patients who have documented anti-HCV treatment for a past HCV infection AND are HCV RNA-negative may be enrolled in the study.
- Have evidence of HIV infection and/or positive HIV antibodies
- Patients with uncontrolled HIV defined as reported CD4+ counts of ≤ 250
- Have had household contact with a person with active TB and did not receive appropriate and documented prophylaxis for TB.
- Have evidence of active TB or latent TB
 - a.) Have evidence of active TB, defined in this study as the following:
 - Positive purified protein derivative (PPD) test (≥ 5 mm induration between approximately 2 and 3 days after application, regardless of vaccination history), medical history, clinical features, and abnormal chest x-ray at screening.
 - QuantiFERON®-TB Gold test or T-SPOT®.TB test (as available and if compliant with local TB guidelines) may be used instead of the PPD test. Patients are excluded from the study if the test is not negative and there is clinical evidence of active TB.
- Have received any of the following medications:
 - a. Biologic treatments for immunologic disease such as etanercept, infliximab, certolizumab, adalimumab, golimumab, tocilizumab, abatacept, ustekinumab, ixekizumab, secukinumab, or anakinra within 8 weeks of screening.
 - b. Cyclophosphamide (or any other cytotoxic agent), belimumab, or anifrolumab (or another anti-IFN therapy) within 12 weeks of screening.
 - c. Rituximab, any other B cell depleting therapies, or intravenous immunoglobulin (IVIg) within 24 weeks of screening.
- Treatment with any other JAK inhibitors within the past 12 weeks

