- Are currently enrolled in or have discontinued within 4 weeks of screening from any other clinical trial involving an investigational product or nonapproved use of a drug or device or any other type of medical research judged not to be scientifically or medically compatible with this study.
- Have had any major surgery within 8 weeks prior to screening or will require major surgery during the study that, in the opinion of the investigator would pose an unacceptable risk to the patient.
- Planning travel that would interfere with study visits.
- Are largely or wholly incapacitated permitting little or no self-care, such as being bedridden or confined to wheelchair.
- In the opinion of the investigator, are at an unacceptable risk for participating in the study.
- Have donated more than a single unit of blood within 4 weeks prior to screening or intend to donate blood during the course of the study.
- Have a history of intravenous drug abuse, other illicit drug abuse, or chronic alcohol abuse within the 2 years prior to screening or are concurrently using, or expected to use during the study, illicit drugs (including marijuana).
- Are unable or unwilling to make themselves available for the duration of the study and/or are unwilling to follow study restrictions/procedures.
- Are investigator site personnel directly affiliated with this study and/or their immediate families. Immediate family is defined as a spouse, parent, child, or sibling, whether biological or legally adopted.
- Have screening laboratory test values, including thyroid-stimulating hormone (TSH), outside the reference range for the population that, in the opinion of the investigator, pose an unacceptable risk for the patient's

Approval Date: 3/16/2022
Principal Investigator: [name]
Application Number: IRB00262268

participation in the study. Patients who are receiving thyroxine as replacement therapy may participate in the study, provided stable therapy has been administered for ≥ 12 weeks and TSH is within the laboratory's reference range. Patients who have TSH marginally outside the laboratory's normal reference range and are receiving stable thyroxine replacement therapy may participate if the treating physician has documented that the thyroxine replacement therapy is adequate for the patient.

- Untreated thyroid, adrenal, or pituitary disease or nodules, or history of thyroid malignancy
- Use of an excluded therapy during the 4-week washout period

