- Have any of the following specific abnormalities on screening laboratory tests from the central or local laboratory:
 - a.) ALT or AST $>2 \times$ upper limits of normal (ULN) ((Treatment should be temporarily interrupted if drug-induced liver injury is suspected) See below for discontinuations.
 - b.) alkaline phosphatase (ALP) $\geq 2 \times$ ULN
 - c.) total bilirubin $\geq 1.5 \times$ ULN
 - d.) hemoglobin $<10 \text{ g/dL}$ (100.0 g/L) (Treatment should be interrupted if Hb $< 8 \text{ g/dL}$ and may be restarted once Hb return above this value)
 - e. total white blood cell count $<3000 \text{ cells}/\mu\text{L}$ ($<3.00 \times 10^3/\mu\text{L}$ or $<3.00 \text{ billion}/\text{L}$)
 - f. neutropenia (absolute neutrophil count [ANC] $<2500 \text{ cells}/\mu\text{L}$) ($<2.50 \times 10^3/\mu\text{L}$ or $<2.50 \text{ billion}/\text{L}$) (Treatment should be interrupted if ANC $< 2 \times 10^9 \text{ cells}/\text{L}$ and may be restarted once ANC return above this value)
 - g. lymphopenia (lymphocyte count $<500 \text{ cells}/\mu\text{L}$) ($<0.50 \times 10^3/\mu\text{L}$ or $<0.50 \text{ billion}/\text{L}$) (Treatment should be interrupted if ALC $< 0.25 \times 10^9 \text{ cells}/\text{L}$ and may be restarted once ALC return above this value)
 - h. thrombocytopenia (platelets $<100,000 \text{ cells}/\mu\text{L}$) ($<100 \times 10^3/\mu\text{L}$ or $<100 \text{ billion}/\text{L}$)
 - i. eGFR $<40 \text{ mL}/\text{min}/1.73 \text{ m}^2$ (Bedside Schwartz formula 2009) or serum creatinine > 1.5 times the ULN

In the case of any of the aforementioned laboratory abnormalities, the tests may be repeated once during screening, and values resulting from repeat testing may be accepted for enrollment eligibility if they meet the eligibility criterion

Approval Date: 3/16/2022
Principal Investigator: [name]
Application Number: IRB00262268

6. Drugs/ Substances/ Devices

- a. The rationale for choosing the drug and dose or for choosing the device to be used.

Drugs:

Abrocitinib 200mg oral tablet – This drug is a study drug that was selected due to its targeting of the Jak1 pathway. 200mg is the dose that has been through Phase 3 trials for treatment of atopic dermatitis and there is significant data available regarding the safety and availability of the drug at this dose.

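### Latent TB is excluded by name but given no test definition, and Section 4a makes the TB test conditional where the schedule does not

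*Combined protocol and SAP*

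**What the plan says.** The TB exclusion in Section 5 opens with "Have evidence of active TB or latent TB". One lettered sub-item follows: "Have evidence of active TB, defined in this study as the following". There is no second sub-item for latent TB; the next bullet deals with prior medications.

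The active-TB sub-item has two parts. The first lists a positive PPD (5 mm or more, whatever the vaccination history) with "medical history, clinical features, and abnormal chest x-ray at screening", and does not say whether all the elements are needed or one is enough. The second says that QuantiFERON or T-SPOT "may be used instead of the PPD test", and then: "Patients are excluded from the study if the test is not negative and there is clinical evidence of active TB".

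Other exclusions give partial cover. One is exposure: "Have had household contact with a person with active TB and did not receive appropriate and documented prophylaxis for TB". Another is general judgement: "In the opinion of the investigator, are at an unacceptable risk for participating in the study". A third covers any active or recent infection that the investigator considers an unacceptable risk.

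On who is tested, Section 4a (Screening Visit) includes a TB assessment for every candidate. It makes the test itself depend on whether it is indicated and on local health practice, and allows a skin or a blood test. The schedule's eligibility row, marked for Visits 1 and 2, lists the PPD with no such condition.

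**The concern.** The heading states an intention and the text beneath it does not carry it out. A positive test in a person without disease is the case in which the word latent has to do its work. For that case the plan gives no criterion, and the one sentence that says what a blood-test result leads to also demands clinical evidence of active disease. The conditional testing in Section 4a adds a second gap, because without a test the heading may have nothing to apply to.

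What is at stake is safety and uniform eligibility. Every participant takes abrocitinib 200 mg daily for 12 weeks, and Section 8 lists serious infection among its risks. No TB test is scheduled after the eligibility row, so the test at screening is the one scheduled chance to find silent infection.

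**Working it through.** No arithmetic applies; the check is to run each written rule on three kinds of candidate, none with clinical evidence of active TB. It assumes that a positive test without disease counts as evidence of latent TB. That is the ordinary meaning, but the plan does not state it.

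The rules:
- Heading: excluded if there is evidence of active or of latent TB.
- Blood-test sentence: excluded if (test not negative) AND (clinical evidence of active TB).
- PPD part, read as all: PPD positive AND history AND features AND abnormal x-ray. Read as any: at least one of these.

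| Candidate | Heading | Blood-test sentence | PPD part |
|---|---|---|---|
| 1. Positive blood test only | Excludes | Not met | Does not apply |
| 2. PPD of 5 mm or more only | Excludes | Does not apply | All: not met. Any: met, and labelled active TB |
| 3. Not tested because not indicated | No test result to act on | Cannot apply | No PPD result to act on |

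Candidates 1 and 2 are kept out by the heading. For candidate 1 the heading and the blood-test sentence do not point the same way, so the outcome depends on which one the site uses. For candidate 2 the all-or-any question alters the label, and alters eligibility only if a site ignores the heading. An indeterminate blood result is less clear still: it is not negative, but it is hard to call evidence of latent TB.

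Candidate 3 arises under the Section 4a text and not under the schedule, which would have a PPD placed. This is the case in which the plan read as a whole gives no protection by test.

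Schedule check: I count 22 rows. One names a TB test (the eligibility row, Visits 1 and 2). None names a chest x-ray, and neither do the screening procedures in Section 4a.

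**The case against.** A reader might infer that the plan permits patients with latent TB to enrol. The documents do not support that. The blood-test sentence gives a condition that is enough for exclusion and does not contain the word only. It sits inside the definition of active TB, and exclusion criteria act separately, so the heading still applies. Where the plan means to admit an intermediate group it says so, as it does for HBcAb-positive, HBV DNA-negative patients and for treated, RNA-negative hepatitis C. It gives no such permission for latent TB. This part of the objection stands and limits the point to a missing definition and a misleading sentence.

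A reader might also infer that some candidates receive no TB assessment, or that nothing watches for TB on drug. Neither follows. The assessment is for everyone and only the test is conditional; a site that follows the schedule tests all. On drug, physical examinations and adverse-event monitoring continue, and Section 4g lets the investigator hold drug for an infection that merits it. These measures bear on active disease during treatment. They would not be expected to reveal a silent infection at entry, which is what a screening test is for.

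The absence of a chest x-ray from the schedule proves little. The criterion itself places the x-ray at screening, and the eligibility row does not claim to be a complete list. The PPD's entry among the study substances in Section 6 shows that it is available, not who receives it.

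The household-contact and investigator-judgement exclusions will remove some patients, but neither turns a test result into a decision.

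**Conclusion.** The point holds in a limited form. Latent TB is excluded in principle and has no working definition. The blood-test sentence, if used as the operating rule, would let through a patient whom the heading excludes. The Section 4a testing condition conflicts with the schedule and can leave the exclusion without a result to act on. The two routes to wrong enrolment are therefore a site applying the sentence instead of the heading, and a site testing only selected candidates under Section 4a.

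The number of candidates affected cannot be worked out from the documents. The conclusion rests on the wording alone and on the assumption that a positive test without disease is latent TB. It is an eligibility and safety correction worth making; it touches no endpoint, analysis or sample size.

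The HIV text is a separate and minor matter. Section 5 excludes all HIV infection, so the bullet on CD4+ counts of 250 or less removes nobody further, and the end-of-drug CD4+ and viral-load test in Section 4a (about 10 mL of blood) has no eligible participant. A reader might infer a dosing risk here. There is none if Section 5 is followed, because the stricter rule governs.

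**What to change.** Two changes are needed.

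1. In Section 4a, require a TB test (PPD or interferon-gamma blood test) for every candidate at screening, and name both options in the schedule's eligibility row.
2. In Section 5, add a sub-item b.): a PPD of 5 mm or more, or a blood test that is not negative, without clinical evidence of active TB, counts as latent TB and is excluded.

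The cost is small. The PPD is already listed as an eligibility test. A skin test has to be read about 2 to 3 days after placement, and no visit falls between Week -4 and Week 0, so a short reading contact is needed. A blood test taken with the Visit 1 draw needs no extra visit. There may be a few more screen failures.

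Optional, for the sponsor to decide:
- One repeat of an indeterminate result. For its own listed laboratory abnormalities Section 5 already says "the tests may be repeated once during screening"; that rule does not extend to TB tests as written.
- An exception for documented treatment of latent TB.
- Stating whether the PPD elements are all required, and naming the chest x-ray as a procedure or deleting it.

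As a separate clean-up, keep one HIV rule. Either retain the blanket exclusion and delete the CD4+ bullet, the CD4 eligibility test and the CD4+/viral-load monitoring, or replace the blanket exclusion with stated CD4+ and viral-load limits and schedule the end-of-drug test.

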Itch Diary Review/compliance			X	X	X	X	X
Skin biopsy		X				X	
Plasma/PBMC isolation from blood draw		X				X	X
Labs from Blood Draw (CMP, CBC, Lipid panel, IgE)	X	X	X	X	X	X	
Patient who are HBcAB-positive and HBV DNA-negative at baseline require HBV DNA monitoring		X	X			X	

Approval Date: 3/16/2022
Principal Investigator: [name]
Application Number: IRB00262268

b. If your study involves data/biospecimens from participants enrolled under other research studies with a written consent or under a waiver of consent, please list the IRB application numbers for those studies. Please note: Certificate of Confidentiality (CoC) protections applied to the data in source studies funded by NIH or CDC will extend to this new study if the funding was active in 2016. If this situation applies, Section 36, question 6 in the application will need to be answered "Yes" and "Hopkins Faculty" should be selected in question 7. No other documents are required.

N/A

c. Study duration and number of study visits required of research participants.

Participants will be in this trial for up to 20 weeks including screening and follow-up.

d. Blinding, including justification for blinding or not blinding the trial, if applicable.

This study will not be blinded. All participants will receive study drug therefore blinding is not applicable.

e. Justification of why participants will not receive routine care or will have current therapy stopped.

Participants will need to stop current therapy in order to qualify for the study. In order to clearly elucidate the efficacy of abrocitinib against PN and CPUO, it is important for concurrent therapies to be halted. It is also important to note that the majority of therapies offered to these patients have poor efficacy in controlling PN and CPUO.

Participants will continue to receive other routine care.

f. Justification for inclusion of a placebo or non-treatment group.

There is no placebo group in this study. As this is an early phase, small study, we will not include a placebo group. If the data is suggestive of efficacy, a full blinded, and placebo-controlled study will be done.

g. Definition of treatment failure or participant removal criteria.

Approval Date: 3/16/2022
Principal Investigator: [name]
Application Number: IRB00262268

Discontinuation Criteria

Discontinuation from Study Treatment

Temporary Interruption of Investigational Product

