Tuberculin PPD – This drug is used as part of a tuberculin PPD test as performed by injecting .1mL of purified tuberculin PPD subcutaneously in the skin. This is the standard dosing for a test to determine if a patient is infected with *Mycobacterium tuberculosis*.

Lidocaine/epinephrine – 3 mL injection at the biopsy site. Lidocaine-HCL 1% w/ epinephrine (1:100,000)

- b. Justification and safety information if FDA approved drugs will be administered for non-FDA approved indications or if doses or routes of administration or participant populations are changed.

N/A

- c. Justification and safety information if non-FDA approved drugs without an IND will be administered.

N/A An IND has been given approval to proceed.

7. Study Statistics

- a. Primary outcome variable.
Percent PP-NRS reduction between baseline and week 12.
- b. Secondary outcome variables.

Analysis of PN-IGA, PROMIS Itch Questionnaire, PAS, 5D Pruritus Score, DLQI, HADS, and EQ-5D and detect differences between baseline through Week 12. An ordinal regression will be used because these are non-parametric, ordinal scales.

Approval Date: 3/16/2022
Principal Investigator: [name]
Application Number: IRB00262268

c. Statistical plan including sample size justification and interim data analysis.

The trial arms of PN and CPUO will be used to conduct subsequent analyses of treatment efficacy. We will treat a p-value of <0.05 as statistically significant, and all tests will be two-tailed. For the primary endpoint, ANOVA will be used to analyze differences in percent PP-NRS reduction (baseline and week 12) with the inclusion of other covariates. We will use a Least-Square means to account for missing data or unbalanced design. We will conduct a two-way analysis of the response variable (PP-NRS percent reduction) by classification variables: specifically, whether the patient has PN or CPUO, and week of treatment. We can derive all LS-means differences from every permutation of week or diagnosis, relative to Week 0 (baseline, prior to treatment). We will incorporate a 95% confidence limit for a significant difference in LS-mean difference between the control group and other groups.

Unlike the primary efficacy endpoint, the secondary endpoints do not have explicit, clinically meaningful changes outlined in the literature. As such, we will look for significant downregulation in itch assessments, and significant improvements in quality of life and sleep measures.

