Secondary aims will be analyzed using appropriate statistical tests as outlined below, and missing data will be corrected with Multiple Imputation (MI) and we will assume that missing data is Missing at Random (MAR).

For secondary analyses, a multivariable logistic regression will be used to calculate the odds ratios of different study arms (PN and CPUO) achieving a 4-point reduction in PP-NRS and in SD NRS.

To analyze the PN-IGA, PROMIS Itch Questionnaire, PAS, 5D Pruritus Score, DLQI, HADS, and EQ-5D and detect differences between baseline through Week 12, an ordinal regression will be used because these are non-parametric, ordinal scales.

IgA for PN is not validated in the US, so we are using it as an additional secondary efficacy measure. Appendix D has a simplified version we are applying to this study. Eczema and psoriasis IgA are similarly qualitative. Analysis of PN/CPUO IgA will be an ordinal scale based on qualitative scaling determined at the site visit. We will analyze IgA with an ordinal regression, same as other scales mentioned above.

Atopy will be defined as a binary variable where patients have 2 out of 3: underlying history of atopic dermatitis, history of seasonal allergies, or asthma.

Among PN patients taking 200 mg of abrocitinib, we will use a linear regression to compare PP-NRS reduction from baseline with week 12, among PN patients with atopy and PN patients without atopy.

Approval Date: 3/16/2022
Principal Investigator: [name]
Application Number: IRB00262268

d. Early stopping rules.

Patients may withdraw at any time or they will be asked to end participation if the physician determines that discontinuation is in the patient's best interest. Data collected may be used if any endpoints are reached.

8. Risks

a. Medical risks, listing all procedures, their major and minor risks and expected frequency.

Foreseeable and known risks of study drug

There is a risk that participants might experience discomfort or side effects with the use of the study drug or procedures. Some of them are still unknown at this stage. In some cases, **side effects can be serious, long-lasting, permanent, or life-threatening**. The study doctor is trained to take the appropriate measures to reduce risks and limit any discomforts you may experience.

Side Effects:

- The most commonly reported side effects are:
 - Nausea (1 in 7 people)
 - Nasopharyngitis (1 in 8 people)
 - Headache (1 in 25 people)
- Rare but serious side effects include:

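### The primary analysis relies on least-squares means to handle missing data; they do not, so the Week 12 result is essentially a completers' mean that may be biased in either direction

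*Combined protocol and SAP*

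**What the plan says.** Section 7a defines the primary outcome as "Percent PP-NRS reduction between baseline and week 12". Section 7c says "ANOVA will be used to analyze differences in percent PP-NRS reduction (baseline and week 12) with the inclusion of other covariates", and then "We will use a Least-Square means to account for missing data or unbalanced design". The classification variables are "specifically, whether the patient has PN or CPUO, and week of treatment". The covariates are not named. No patient effect, within-patient covariance, missingness assumption, analysis population or sensitivity analysis is given for this endpoint.

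Later in Section 7c, in a sentence that opens with the secondary aims, "missing data will be corrected with Multiple Imputation (MI) and we will assume that missing data is Missing at Random (MAR").

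Under Section 7d patients may leave when they wish, or "they will be asked to end participation if the physician determines that discontinuation is in the patient's best interest". It adds: "Data collected may be used if any endpoints are reached". Section 4d and Section 4f make the trial open-label with no placebo group, and Section 4f looks ahead: "If the data is suggestive of efficacy, a full blinded, and placebo-controlled study will be done". The visit table in Section 4a schedules PP-NRS at Weeks 0, 2, 4, 8, 12 and 16.

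**The concern.** The second half of the least-squares-means claim is right and the first half is wrong. These means re-weight cells that differ in size and adjust for covariates in the model. A patient without a Week 12 value contributes nothing to the Week 12 cell. With only diagnosis and week as factors, that patient's Week 2, 4 and 8 values inform the means of those weeks and essentially nothing else.

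The secondary endpoints therefore have an explicit method and assumption for missing data, while the primary endpoint has a device that does not do the job claimed for it. There is no comparator arm in which a similar bias might partly cancel, and the decision on a placebo-controlled study is tied to these data. The direction cannot be known in advance: dropout of poor responders flatters the result, dropout of good responders understates it, and dropout unrelated to response leaves it about right.

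**Working it through.** **Inputs.** The endpoint, model factors and visit weeks come from Sections 4a, 7a and 7c. The documents give no sample size, SD, expected effect or dropout rate, so there is no planned figure to reproduce. Every numerical input below is an assumption.

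**Step 1: what the stated model estimates.** With diagnosis, week and their interaction as factors, the Week 12 least-squares mean is

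½ × (mean of observed PN values at Week 12 + mean of observed CPUO values at Week 12).

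- In a simulated set of 20 patients with 20% dropout, the model gave 61.79, and the average of the two diagnosis-specific completer means was also 61.79. A main-effects model and a Week 12-only ANOVA gave the same value.
- In 40 simulated sets of 200 patients (within-patient correlation 0.6, about 24% dropout, poor responders leaving, true value 50), the least-squares mean and the completers' mean were both 54.4. A main-effects model differed by at most 0.2 points. Adding a random patient intercept gave 50.1 (SE 0.4).

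So the patient term makes the difference, and the plan does not state one.

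**Step 2: bias by arithmetic.** With dropout fraction d, bias = d × (completer mean − mean the dropouts would have had). For d = 0.20 and a completer mean of 50:

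- dropouts would have had 10: 0.20 × (50 − 10) = +8 points;
- dropouts would have had 80: 0.20 × (50 − 80) = −6 points.

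**Step 3: bias by simulation.** Assumed mean reductions are 25/35/45/50% at Weeks 2/4/8/12, with SD 30 at each visit and equal within-patient correlation of 0.5 to 0.7. Dropout after Weeks 2, 4 and 8 depends on the last observed value, with an odds ratio of 2 to 4 per SD (200,000 patients per scenario). The table shows the error of the completers' mean, in percentage points, against a true 50:

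| Total dropout | Poor responders leave | Good responders leave | Unrelated |
|---|---|---|---|
| 10% | +1.1 to +2.6 | −1.0 to −2.6 | within 0.1 |
| 20% | +2.2 to +5.0 | −2.0 to −5.0 | within 0.1 |
| 30% | +3.4 to +7.4 | −3.2 to −7.4 | within 0.1 |

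A likelihood model using all post-baseline visits gave 50.0 to 50.1 throughout. That is expected, because these data are missing at random by construction.

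**Step 4: a sharper dropout mechanism.** Here the correlation is 0.7, all dropouts are lost after Week 4, and dropout is driven strongly by the Week 4 value (6,000 patients per scenario). Errors at 10/20/30% dropout were +3.7/+6.3/+8.9 when poor responders leave and −3.4/−6.2/−8.6 when good responders leave. When dropout depended on the unseen Week 12 value, they were +5.1/+8.9/+12.1. In that last case at 20% dropout the truth was 49.8, the ANOVA gave 58.7 and a mixed model gave 53.6. A model that assumes missing at random helps but does not remove the bias.

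**Step 5: the Section 7d sentence.** Suppose it means that a withdrawn patient's data count only if an endpoint was reached, taken here as a reduction of at least 50% at any visit. The completers' mean does not change, because withdrawn patients have no Week 12 value. The likelihood estimate at 20% dropout, however, is then off by +2.7 to +5.2 (poor responders leave), +1.4 to +1.8 (unrelated) or +0.1 to +0.6 (good responders leave). On that reading, Section 7d would undo the repair.

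**The case against.** The strongest reply is that the plan is brief rather than wrong. A two-way analysis by diagnosis and week already brings all visits into the model, and least-squares means from a model with a patient effect would be sound under missing at random. That is true. But the text states no such effect, and the validity of the primary estimate depends on it.

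The multiple-imputation clause could be meant to cover everything. Its sentence is about secondary aims, though, and what follows are secondary analyses. One of them, the 4-point PP-NRS reduction, uses the same instrument, but it yields odds ratios between diagnoses and not the mean Week 12 reduction.

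Materiality is a fair challenge. Section 4f calls the study small. With SD 30 and an assumed 20 patients, the standard error is 30/√20 = 6.7 points, or 30/√16 = 7.5 after 20% dropout. With 40 patients it is 4.7, or 5.3 after dropout. Most of the illustrated biases at 10% to 20% dropout are below one standard error. This limits the weight of the point. It does not justify the claim in the plan, because the confidence interval reflects sampling error and not this bias.

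Two further reservations stand. The stopping rules in Section 4g concern the study drug and do not say that itch scores stop being collected, so they are weak evidence that Week 12 values will be missing. The Section 7d sentence is permissive and ambiguous, and the main point does not depend on it.

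**Conclusion.** The concern holds and should be fixed before analysis. As written, the Week 12 primary estimate is essentially a completers' mean, and the device named for missing data does not address them. The word essentially is needed: the two diagnoses are weighted equally, and covariates, if they explain dropout, could remove some bias, but none is named.

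The conclusion about the method follows from the text. The size does not. Under the assumptions above, the error at 20% dropout is roughly 2 to 6 points in either direction when dropout depends on observed response, more if it depends on unseen response, and near zero if unrelated. No efficacy threshold is stated, so a changed decision cannot be shown.

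**What to change.** - In Section 7c, delete the claim that least-squares means account for missing data.
- Analyse all dosed patients with a likelihood-based repeated-measures model on every post-baseline visit through Week 12, and state the patient effect or covariance structure. Percent reduction is zero for everyone at Week 0, so the Week 12 mean is already the contrast with baseline. Week 0 should not enter as an outcome: in the sharper simulation at 20% dropout of poor responders, including it in a random-intercept model gave 52.2 against a true 49.5, while post-baseline visits alone gave 49.7.
- Alternatively, extend the plan's own multiple imputation to the primary endpoint, with diagnosis and the Week 2, 4 and 8 PP-NRS in the imputation model. The daily diary itch ratings could be added.
- Add a sensitivity analysis under departures from missing at random, for example counting withdrawals as 0% reduction. This is deliberately severe: at 20% dropout it gives 0.8 × 45 = 36 to 0.8 × 55 = 44 against an assumed 50. It is a check on the result, not a replacement for the primary estimate.
- In Section 7d, state that all data collected up to withdrawal are analysed for every dosed patient, whether or not an endpoint was reached.

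The cost is rewording two sections and some added analysis. PP-NRS is already scheduled at every visit needed.
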